## 1. AMENDMENT HISTORY

Amendment No.	Protocol Version No.	Date issued	Author(s) of changes	Details of Changes made
1	2	18/02/2021	[name]	
 
• Amendment to inclusion and exclusion criteria
 
• Further detail of informed consent process added
 
• Further detail on safety SOP's added
 

2	3	10/05/2021	[name]	
 
• Wording change of “nurses” to “UoP staff”
 
• Identification of where screening blood samples will be analysed added.
 

## 2. SYNOPSIS

Study Title	The Effect of Chronic Passive Heating on Insulin Sensitivity and Cardiovascular function in People with Type 2 Diabetes Mellitus: A pre- and post-test trial.
Internal ref. no.	n/a
Problem statement	
Type 2 diabetes mellitus (T2DM) is a metabolic condition characterized by chronic hyperglycemia and progressive insulin resistance, which progressively lead to macro- and microvascular damage and subsequent impairments in blood pressure (BP) control. Therapeutic approaches to manage T2DM focus on improving glycaemic control and BP and include pharmaceutical treatments (e.g. Metformin and insulin), physical activity and exercise, and calorie restriction. However, pharmaceutical interventions can be expensive and are associated with low adherence. Although exercise and diet programs have been shown to be effective, like pharmaceutical interventions, they often have poor adherence in people with T2DM. With the number of people with T2DM (464 million) continuing to rise and expected to reach 700 million by 2045, the costs associated with the clinical management of this condition are likely to become unsustainable. There is, therefore, a need to explore the potential of alternative interventions. In particular, interventions which may be cheaper than clinical management and have better adherence than exercise, and hypoglycemic agents, to improve glycemic control and deleterious cardiovascular manifestations of this condition.

	Passive heating may be one such intervention with therapeutic potential.
Research question / hypothesis	
Before passive heating can be considered as a therapeutic option for improving metabolic and cardiovascular health in individuals with T2DM, we need to explore whether their chronic passive heating (1h x 10 days) is able to improve:
 
 
1) insulin sensitivity
 
2) glycaemic control
 
3) metabolic efficiency
 
4) vascular health
 

Study Design	We plan to run a within-subject, pre-, post-intervention study
Study Participants	Adults $\geq$ 35 years (post-menopausal for females), diagnosed with T2DM as defined by the world health organisation (WHO).
Planned Sample Size	We aim to recruit 20 individuals with T2DM.
Follow-up duration	7 days
Planned Study Period	18 months
Primary Objective	To determine whether chronic passive, warm water therapy increased insulin sensitivity in individuals with T2DM?
Secondary Objectives	
To determine whether chronic passive, warm water therapy improves:
 
 
1) glycaemic control
 
2) metabolic efficiency
 
3) vascular health
 

Primary Endpoint	Improvement in insulin sensitivity from chronic passive heating.
Secondary Endpoints	

1) fasting plasma [glucose]

2) AUC plasma [glucose]

3) peak plasma [glucose]

4) HbA1c

5) plasma [eHSP70]

6) plasma [IL-6]

7) plasma [IL-10]

8) plasma [butyrate]

9) plasma [growth hormone]

10) RMR

11) fat oxidation

12) CHO oxidation

13) macrovascular function

14) microvascular function

15) resting heart rate

16) stroke volume

17) total peripheral resistance

	18) cardiac output  19) heart rate variability
Intervention (s)	8-12 x1 h water immersion (to the clavicle, @40 °C, rectal temperature ~38.5 °C and <39 °C) sessions over a period of 14 days.

### 3. ABBREVIATIONS

AE	Adverse event
ANOVA	Analysis of variance
AUC	Area under the curve
CHO	Carbohydrate
CPET	Cardiopulmonary exercise test
CRF	Clinical records file
ECG	Electrocardiogram
EDTA	Ethylenediaminetetraacetic acid
eHSP	Extracellular heat shock protein
GCP	Good clinical practise
GH	Growth hormone (human)
Hb	Haemoglobin
HbA1 c	Haemoglobin adult type 1 c (Glycated haemoglobin)
Hct	Haematocrit
HEC	Hyperinsulinaemic-euglycaemic clamp
HIIT	High intensity interval training
HR	Heart rate
HRV	Heart rate variability
HSP	Heat shock protein
IL	Interleukin
LF	Low frequency
NHS	National Health Service
NIHR	National institute for health research
NIRS	Near infrared spectroscopy
NRES	National research ethics service
OGTT	Oral glucose tolerance test
PCPI	Patient, carer and public involvement
PPI	Patient public involvement
QUICKI	Quantitative insulin sensitivity check index

REC	Research ethics committee
RHR	Resting heart rate
RMR	Resting metabolic rate
RMSSD	Root mean square of the successive differences
RSA	Respiratory sinus arrhythmia
SAE	Serious adverse event
T2DM	Type 2 diabetes mellitus
T rec	Rectal temperature
UoP	University of Portsmouth
VO 2	Oxygen consumption
WHO	World health organisation

#### 4. BACKGROUND AND RATIONALE

Current estimates suggest 422 million people worldwide live with a form of diabetes, of which ~ 90% have type 2 diabetes mellitus (T2DM) [1]. The total direct and indirect cost of care for individuals with diabetes in the UK is £23.7 billion, equating to ~ 20% of the annual NHS budget [2], this figure is expected to rise to ~£39.8 billion by the year 2035 [2, 3]. Approximately 85-90% of cases of T2DM arise from a poor lifestyle and obesity [4-6], with the remaining 10-15% resulting from genetic predispositions [7, 8]. Current interventions include pharmaceutical treatments, exercise and calorie restrictive diets, which aim to improve glycaemic control. However, pharmaceutical interventions carry a high financial cost [9, 10], while exercise and diet programmes have a low adherence rate in individuals with T2DM [10-15]. With the prevalence of T2DM continuing to increase, the costs associated with the clinical care of these individuals are likely to become unsustainable. Simple, inexpensive interventions to improve the clinical profile of this group are therefore needed.

One emerging potential therapy to improve glucose homoeostasis is passive heating. Preliminary evidence suggests passive heating may have beneficial effects for metabolic health in animal models [16-21] and in humans [17, 22-24]. In 1999, the use of hot tubs (38-41°C, 30 mins / day for 3 weeks) was shown to reduce fasting plasma glucose concentrations by ~14% (1.3 mmol.L) and decrease HbA1c by ~10-11 mmol/mol in 8 individuals with T2DM [23]. Given the rate of turnover in haemoglobin this reduction is surprising as the treatment period was run over 3 weeks and the total haemoglobin turnover takes ~115 days [25]. While more recent work has been conducted into the effects of a single bout of passive heating in healthy adults [22] and individuals with T2DM (including ourselves, under review) [22, 24], none have been done on chronic heating since Hooper [23]. Hooper [23] postulated that an increase in skeletal muscle blood flow may be responsible for this increased glucose clearance, citing evidence that this can modulate insulin mediated glucose uptake [26]. Other mechanisms have also been purported, but have yet to be elucidated, including; increased insulin sensitivity [27, 28], altered inflammatory response [29-31], activation of heat shock proteins (HSP) [32], altered gut microbiome and butyrate [33]. Repeated passive heating results in transient increases in deep body temperature [24, 34-37] and may improve glucose homeostasis [22, 38-46] via similar mechanisms to exercise.

Regular aerobic exercise also improves macro- [47] and microvascular function [47], muscle oxygenation [48], autonomic function [49], cardiorespiratory fitness [50], lung function [51] and delays age related muscle loss [52]. Acute exercise studies show that insulin sensitivity after 1h of moderate exercise does not change [53, 54], however, insulin sensitivity appears to be improved following bouts longer than an hour [54] or performed at greater intensity [55]. Increases in insulin sensitivity have a curvilinear relationship with energy expenditure [54] and could also be due to greater HSP expression [56]. However, it is unrealistic for people with T2DM to perform this level of activity. Passive heating may be one supplemental exercise

mimetic to augment improvements in insulin sensitivity, cardiorespiratory fitness [60] and muscle strength, and function [81].

We recently provided evidence that acute passive heating in people with T2DM (currently under review for publication) is well tolerated and increases extracellular [HSP70], and energy expenditure, and reduce diastolic blood pressure. There is a growing body of evidence that suggests passive heating may improve many facets of human physiology, however, the mechanisms that underpin these benefits have yet to be established and future research needs to explore these further.

## **6. AIMS AND OBJECTIVES**

This study will provide us with important data that will help ascertain whether passive heating has the potential to be used as a future treatment for T2DM and also provide mechanistic insight to how passive heating effects individuals with T2DM.

### **6.1 Primary Objective**

To determine whether chronic passive heating can increase insulin sensitivity in individuals with T2DM.

## 6.2 Secondary Objectives

To establish if chronic passive heating improves:

- 1) glycaemic control
- 2) metabolic efficiency
- 3) vascular health

## 7. STUDY DESIGN

### 7.1 Summary of study design

**Plan of investigation:** We plan to run a pre-, post-intervention study to assess chronic heating's effect on metabolic health and cardiovascular function in people with T2DM. We aim to recruit 20 individuals with T2DM. All visits (11-15) will take place within our physiology laboratories (Spinnaker Building, University of Portsmouth). The experimental design will involve an initial screening visit (~1 h), two identical experimental visits (pre and post intervention) (~3 h) and 8-12 intervention visits (~1.5 h) (see Figure 1). We will aim for 10 intervention visits [57], however for feasibility we have incorporated scope for plus or minus 2 immersions for individuals who want to come for extra visits or struggle with time constraints. Both longer [58] and shorter protocols [59] have been utilized in the past. The screening visit will consist of participant characterisation, safety assessments including resting electrocardiogram (ECG), screening bloods (HbA1c, FBC, liver and renal function) and familiarisation with the testing procedures. On experimental visits, the participants will arrive at 0800 in a fasted state (12 h), and will have refrained from exercise 48 h before, alcohol and caffeine 24 h before, and taking any diabetes medication the morning of the visit. Participants will then undergo: baseline measurements of bloods, central haemodynamics, RMR, macro- and microvascular function; then an oral glucose tolerance test (OGTT) and re-measurements of blood (for analysis of plasma [glucose] and [insulin] only here). After the OGTT participants will be provided with a snack.

The intervention visits consist of the participant being immersed into a 40 °C hot tub for 1 h with rectal temperature measured throughout to ensure target deep body temperature is attained (38.5 - 39°C) and to also monitor deep body temperature for safety (see 10.5). To clamp deep body temperature, body position in the hot tub will be manipulated accordingly to allow heat loss to occur. If rectal temperature goes above 39 °C the heating protocol will be terminated and cool procedure enacted. Visit measurements and time course are explained in detail in section 10.6.

[figure not shown]
**Participants and Recruitment:** A power calculation indicates (looking for a difference in paired means) that 15 people are required to detect a 1 standard deviation change in insulin sensitivity ( $\alpha = 0.05$ ; power = 80%). Given the magnitude of change shown in other chronic passive heating studies [60] it is not unreasonable to expect to see this effect size (see 10.1). To account for participant drop-out we intend to recruit 20 people aged  $> 35$  years with T2DM (as defined by the World Health Organisation (WHO), with an HbA1c  $> 48$  (mmol/mol). Participants will be excluded from the study if they have uncontrolled hypertension (systolic blood pressure  $> 180$  mmHg); a history of myocardial infarction or cerebrovascular events; leg ulcers; unable to give informed consent or any other serious medical condition which would interfere with safety or data interpretation.

Participants will be recruited from a database of known individuals with T2DM who attend outpatient clinics at the Queen Alexandra Hospital (Portsmouth) and via posters and word of mouth within the University of Portsmouth. We will also recruit from local GP practices via mail outs.

**Consent and Screening:** Visit 1 will act as a screening, consent and familiarisation ( $\sim 1$  h). Participants will be given the opportunity to ask any questions they may have after reading the participant information sheet. A standard medical history and clinical examination will be undertaken by a member of UoP staff, including for example height, mass, electrocardiogram, ankle-brachial pressure index and blood sample collection for lipids and biochemical markers, and liver function tests. Seated resting blood pressure measurements will be performed to calculate systolic, diastolic blood pressure.

### Will you obtain informed consent from or on behalf of research participants?

A member of the UoP research team will take consent for all subjects. These individuals are familiar with the principles underpinning informed consent and methods to assess capacity to give consent, for example asking the participant to summarise what the study involves for them. Only participants who have capacity to consent to taking part in research will be recruited into the study. If the researchers are in any doubt they will not be consented. The research staff will endeavour to keep the participants informed throughout the study and will encourage participants to ask questions about any uncertainties throughout their involvement in the study.

**Figure 1.** Study overview. OGTT = oral glucose tolerance test. \*measurements at baseline will be blood (biomarker analysis detailed in 10.6), central haemodynamics and resting metabolic rate. At the end of OGTT only blood will be taken again for the measurement for the analysis of plasma [glucose] and [insulin].

## 7.2 Primary and Secondary Endpoints/Outcome Measures

The primary outcome of this study is insulin sensitivity. Secondary outcomes are:

- 1) fasting plasma [glucose]
- 2) AUC plasma [glucose]
- 3) peak plasma [glucose]
- 4) HbA1c
- 5) plasma [eHSP70]
- 6) plasma [IL-6]
- 7) plasma [IL-10]
- 8) plasma [butyrate]
- 9) plasma [growth hormone]
- 10) RMR
- 11) fat oxidation
- 12) CHO oxidation
- 13) macrovascular function
- 14) microvascular function
- 15) resting heart rate
- 16) stroke volume
- 17) total peripheral resistance
- 18) cardiac output
- 19) heart rate variability

### 8.2 Overall Description of Study Participants

Participants will be adults with a clinical diagnosis of T2DM, as defined by the WHO. A standard medical history and clinical examination will be undertaken by a member of UoP staff. Information taken during the examination will be height, weight, full blood count (analysed from a blood sample that will be collected), HbA1c and a resting ECG. ECG will be examined for irregularities and a clinical decision will be made on further participation to the study by a consultant at QA hospital.

## 9. SAMPLING

An *a priori* sample size calculation was performed based on a passive heating study assessing insulin sensitivity in health individuals [60]. The mean difference between pre and post chronic passive heating was  $16 \pm 14.5$  a.u. for insulin sensitivity ( $\sim 1\text{SD}$ ). For 80% power and an  $\alpha$ -

level set at  $P = 0.05$  (two tailed), to detect a 1 SD difference 15 individuals are required. In order to account for dropout, we anticipated that 20 individuals would need to begin the study.

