## **10. STUDY PROCEDURES**

### **10.1 Recruitment**

Our typical recruitment rates via GP practices is approximately one in ten people with T2DM. Recruitment via the local DESMOND course (T2DM education clinic) is approximately one in five people with T2DM. We will need to approach between 90 and 113 people with T2DM to ensure we recruit enough ( $n = 15$ ) people to account for drop outs.

Recruitment will be carried out by members of the UoP research team (or clinical team if participant clinical records are needed) acting with appropriate contracts with the responsible care organisation. The clinical staff will be briefed in detail regarding the current project and they will be provided with the inclusion and exclusion criteria of the study in order to perform any database searches. In the case of the computerised search of GP databases, this will be conducted by the direct healthcare team. Following receipt of the reply slips to the UoP research team, consent and screening will take place and results forwarded (for those willing) to our consultants who will review the results against the inclusion / exclusion criteria. Posters and word of mouth will also be utilised. Screening blood will be analysed at QA pathology or at a commercial pathology laboratory.

Inclusion criteria:

- Male or female (post-menopausal) aged 35 years or above.
- Diagnosed with T2DM as defined by the WHO ( $\geq 48$  mmol/mol).
- Participant is willing and able to give informed consent for participation in the study.
- Participant is able to understand and fully cooperate with the study protocol.

Exclusion criteria:

- Severe peripheral neuropathy (to the point to which they cannot sense temperature)
- Uncontrolled hypertension ( $\geq 180$  systolic / 100 diastolic mmHg)
- Taking any medication which may interfere with data interpretation or safety
- Who have had a myocardial infarction or cerebro-vascular event
- Any cardiac abnormalities which restrict hard exercise

- Current smokers or who have stopped within 3 months
- Participant is unable to understand and/or fully cooperate with the study protocol
- Any other serious medical condition which would interfere with data interpretation or safety will be excluded from participation.
- Skin ulcerations
- Eczema
- Pre-existing postural hypertension
- Existing cardiac diseases (identified during screening)

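### The 15 completers required for a 1 SD paired change do not follow from the stated inputs (10 suffice if 14.5 is the SD of the change), and section 10.1 recruits 15 where the rest of the protocol recruits 20

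*Combined protocol and SAP*

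**What the plan says.** Section 7.1 describes a power calculation for a difference in paired means and states that "15 people are required to detect a 1 standard deviation change in insulin sensitivity", at alpha 0.05 and 80% power. It then says "it is not unreasonable to expect to see this effect size (see 10.1", which sends the reader to section 10.1 for support.

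Section 9 gives the source, a passive heating study in healthy people: "The mean difference between pre and post chronic passive heating was" 16 ± 14.5 a.u., described as about 1 SD. With a two-tailed test at 0.05 and 80% power, "to detect a 1 SD difference 15 individuals are required". Section 14.2 names the paired t-test as the analysis, with the Wilcoxon signed-rank test if the data are not normal.

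On numbers recruited, the synopsis and section 7.1 both say "We aim to recruit 20 individuals with T2DM". Section 7.1 adds "To account for participant drop-out we intend to recruit 20 people aged", and section 9 says "In order to account for dropout, we anticipated that 20 individuals would need to begin the study". Section 10.1 differs: "We will need to approach between 90 and 113 people with T2DM to ensure we recruit enough", with n = 15 given as the number that already covers dropout. It quotes yields of about one in ten through GP practices and one in five through the DESMOND course.

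**The concern.** Section 14.4 says that no separate analysis plan is needed, so these paragraphs are the only justification of the sample size. A paired test for a full 1 SD change normally needs about 10 people, so 15 at 80% power looks wrong for the stated inputs. The size and direction of the error depend on what 14.5 is, and the protocol does not say. A reader therefore cannot tell what change the trial can detect.

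Section 10.1 uses 15 as the number to recruit, whereas in section 9 it is the number left after dropout. If section 10.1 were followed, the trial would start with too few people for its own requirement. Its approach figure would also understate the work to be done in the recruitment window of section 18 (February to October 2021).

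**Working it through.** **Inputs.** Paired comparison, two-sided alpha 0.05, power 80%, effect 1 SD (sections 7.1 and 9). Source values 16 and 14.5, ratio 16/14.5 = 1.10 (section 9). Paired t or Wilcoxon (section 14.2). 20 starters for 15 completers, an implied loss of 1 − 15/20 = 25%. Yields of 1 in 10 and 1 in 5, and 90 to 113 approaches (section 10.1).

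**Step 1: 14.5 as the SD of the paired change.** Power is the probability that a noncentral t with n − 1 degrees of freedom and noncentrality d√n falls outside ± the 0.975 point of the central t.

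| Completers | Power, d = 1 | Power, d = 1.10 |
|---|---|---|
| 8 | 68.1% | 76.3% |
| 9 | 74.8% | 82.5% |
| 10 | 80.3% | 87.3% |
| 11 | 84.8% | 90.9% |
| 15 | 94.9% | 97.8% |
| 20 | 98.9% | 99.7% |

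The requirement is 10 at 1 SD and 9 at 1.10 SD. At 80% power, 15 completers detect 0.78 SD, or 0.778 × 14.5 = 11.3 a.u. By simulation with normal changes and d = 1, the Wilcoxon test has about 78–79% power at 10 and 81% at 11, so the fallback needs about 11 and does not explain 15.

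**Step 2: other routes to 15.** Changing a stated input comes near but does not reach it at d = 1: 90% power gives 13, 95% power gives 16, alpha 0.01 gives 16, and a two-sample formula gives 16 to 17 per group.

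**Step 3: 14.5 as a single-visit SD.** With pre-post correlation r, the paired effect is d/√(2(1 − r)).

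| r | n for d = 1 | Power with 15, d = 1 | n for d = 1.10 |
|---|---|---|---|
| 0 | 18 | 72.2% | 15 |
| 0.2 | 15 | 81.2% | 13 |
| 0.5 | 10 | 94.9% | 9 |
| 0.8 | 6 | >99.9% | 5 |

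Exactly 15 results for r from 0.17 to 0.24 at 1 SD, and for r from 0 to 0.07 at 1.10 SD. The stated figure can therefore be reached, but only with a correlation and an SD basis that the protocol does not give.

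**Step 4: the cross-reference.** Section 10.1 is Recruitment and holds no effect size. The effect size is in section 9.

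**Step 5: recruitment.** The step from 15 to 20 is consistent: 15/(1 − 0.25) = 20. If section 10.1's 15 were the number starting, the same loss would leave 15 × 0.75 ≈ 11 completers, with 84.8% power for 1 SD under step 1, or 65.7% under step 3 with r = 0.2.

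Yield of 90 to 113 approaches at the two stated rates:

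- GP practices only: 90/10 = 9 to 113/10 ≈ 11.
- DESMOND only: 90/5 = 18 to 113/5 ≈ 23.
- Equal recruits from each, averaging (10 + 5)/2 = 7.5 approaches per recruit: 90/7.5 = 12 to 113/7.5 ≈ 15.
- Equal numbers approached, averaging 15%: 90 × 0.15 = 13.5 to 113 × 0.15 ≈ 17.

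The printed range matches 12 × 7.5 = 90 and 15 × 7.5 = 112.5, so it fits 12 to 15 recruits. On these two routes, 90 approaches cannot yield 20. With 113, at most 2 of the 20 can come from GP practices: 2 × 10 + 18 × 5 = 110, but 3 × 10 + 17 × 5 = 115. Twenty recruits need 20 × 5 = 100 to 20 × 10 = 200 approaches: 150 with equal recruits (20 × 7.5), or 133 with equal approaches (20/0.15).

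**The case against.** The strongest defence is that section 7.1's wording can be read as a change of one SD of the measure itself, which makes 14.5 a visit SD. With 16, 14.5 and zero correlation, the paired effect is 1.10/√2 = 0.78, and exactly 15 are needed (80.2% power). On that reading the fault is an unlabelled SD and not a wrong sum. The source study cannot be consulted here to settle it.

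That possibility stands, and it is why the SD must be labelled before any figure is changed. It is the less natural reading, because section 9 attaches 14.5 to the mean pre-post difference. It also assumes no correlation between two measurements on the same person, and it uses the unrounded 1.10 where both sections say 1 SD. At 1 SD and zero correlation, 18 are needed.

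Three further points are fair. The case of 11 completers is not the planned trial, since 20 starters appear in four places. It shows only what follows if section 10.1 is taken literally. The recruitment arithmetic covers two routes, while the protocol also names the outpatient database, posters and word of mouth, so the shortfall in approaches is shown only at the two stated rates, which are approximate. And nothing here changes the number enrolled or the analysis. That limits the weight of the point, but the figures still need correcting.

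**Conclusion.** The point holds. If 14.5 is the SD of the change, 15 overstates the requirement by 5 completers. The error is conservative, and the trial is not underpowered for its own assumed effect. If 14.5 is a visit SD, 15 is right only for a narrow band of low correlations, too many above that band, and at 1 SD too few below it. The protocol does not let a reader choose between these.

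The conflict between 15 and 20 recruits does not depend on any reading of the SD. Section 10.1 is the outlier, and the target of 20 is not in doubt. Its approach figure fits about 12 to 15 recruits if the two routes supply equal numbers. These conclusions assume normally distributed changes, the implied 25% loss, and the two yields printed in section 10.1.

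**What to change.** Keep 20 starters, and make these wording changes:

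- **Sections 7.1 and 9:** state first what 14.5 is. If it is the SD of the paired change, say that 10 completers give 80% power for 1 SD, and that 15 give 95% for 1 SD and 80% for 0.78 SD (11.3 a.u.). If it is a visit SD, keep 15 and state the correlation, and whether 1 or 1.10 SD was used.
- **Section 7.1:** point the effect-size reference to section 9.
- **Section 10.1:** change n = 15 to n = 20. Give 100 to 200 approaches with the assumed split between routes (about 150 if GP practices and DESMOND supply equal recruits). Say that this leaves out the outpatient database, posters and word of mouth, for which no yield is given.

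The cost is text in three sections. No participant, procedure or analysis changes. The stated approach figure becomes less favourable.
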